For transiting from Cohort M1 to M2, the sponsor will discuss with the medical expert based on the "Results of Safety Evaluation up to 48 Hours Post-dose (During Hospitalization)," "Investigator's View on Transition to the Next Cohort," and "Plasma Unchanged Drug Concentrations up to 24 Hours Post-dose\*" collected up to S6 and M1 and will obtain the "Medical Expert's View on Transition to the Next Cohort." Upon reaching a determination on whether or not to transit to Cohort M2, along with the dose duration, and frequency of administration, the sponsor will prepare the "Notification of Transition to the Next Cohort and Dosing Regimen," and submit the form to the investigator with the "Plasma Unchanged Drug Concentrations up to 24 Hours Post-dose.\*" The investigator will inform the sponsor regarding whether or not he/she agrees with the above sponsor's view using the "Cohort Transition Agreement Record," along with the reason if he/she disagrees. If the investigator's agreement is obtained, the sponsor will instruct to transit to Cohort M2. If the investigator disagrees, the sponsor will hold discussions with the investigator until an agreement is reached. Upon reaching an agreement, the sponsor will either instruct to transit to Cohort M2 with the determined dose or discontinue the study.

\*: The report includes a list of plasma unchanged drug concentrations,  $C_{max}$ , and AUC by subject.

(3) Discontinuation of cohort transition

If any of the following conditions are met in either Part 1 or Part 2, the sponsor, the medical expert, and the investigator will hold a discussion and stop the cohort transition and administration (only in Part 2), except for cases in which a reasonable reason exists. Whether subjects are allocated to the active or placebo group will be checked using the table of randomization key codes.

- 1) At least 1 subject in the active group has experienced a serious or severe adverse event (AE) in one cohort, and the investigator (or subinvestigator) has determined that the AE is "reasonably related" to the study drug.
- 2) At least 1 subject in the active group has any of the following laboratory results in one cohort.
  - ALT or AST  $\geq 3 \times$  upper limit of normal (ULN) and total bilirubin  $\geq 2 \times$  ULN
  - Serum creatinine  $\geq 2 \times$  ULN
- 3) At least 1 subject in the active group has any of the following 12-lead ECG results in one cohort.
  - QTcF  $\geq 500$  ms

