  - Increase in QTcF by  $\geq 60$  ms from baseline

All discussions and decisions shall be recorded with the signature of the sponsor and/or the investigator. The originals and copies of the records will be retained by the sponsor and study site, respectively.

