### 9.2.6 Pharmacodynamic Assessments

Holter ECG data will be collected at the time points shown in the table below. The investigator (or subinvestigator) will record the conduct of the test in the CRF.

Each subject will wear the Holter monitor from at least 1 hour pre-dose to the completion of recording at 48 hours post-dose.

Additional details regarding the procedures are specified in a separate procedure.

Part 1  (single-dose study)

• Day 1: 45, 30, and 15 minutes pre-dose, 15 and 30 minutes post-dose, and 1, 1.5, 2, 4, 6, 8, and 12 hours post-dose

• Day 2: 24 and 36 hours post-dose

- Day 3: 48 hours post-dose

: For Cohorts S4, S5, and S6

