## 13. Statistical Analysis

### 13.1 General Requirements

Detailed statistical analysis procedures will be documented in a separate Statistical Analysis Plan. The Statistical Analysis Plan will be prepared and fixed prior to data lock. In addition, all individual subject data will be listed.

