### 13.3 Data Handling

The data will be handled as described below, except for cases determined in the sponsor's case conference or at the conference for the handling of drug concentration data. The handling of the safety, drug concentration, and PD data will be specified in the Statistical Analysis Plan or the Clinical Study Report.

[1] Definition of the baseline for the safety and PD assessments

Unless otherwise specified, the baseline for these assessments is the last data measured prior to the start of study drug administration.

[2] Handling of analysis data for each time point

The acceptable time range for each measurement time point will be specified in the Statistical Analysis Plan, and the data collected within the time range will be used. Data will not be imputed by data collected outside the time range. If multiple data exist within the same time range for one assessment item, the data collected later will be used.

[3] Handling of unmeasurable data and reference data in laboratory tests

If unmeasurable or reference data are obtained due to specimen problems, they will be handled as missing data.

[4] Handling of PK data

The acceptance time range for each blood sampling timepoint for determining the plasma drug concentrations will be specified in the Statistical Analysis Plan. The sponsor will judge the handling of the following data, as to whether or not to include them in the tabulation and analysis of the drug concentrations: (1) data that was

collected from a blood specimen drawn outside of the acceptance time range; (2) data for which the plasma drug concentration was unmeasurable; and, (3) data for which a protocol deviation occurred, such as non-compliance with plasma collection procedures. The handling of data will be decided at the case conference or at the conference for the handling of PK data.

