### **13.4 Statistical Analysis Plan**

Analytical variables will be classified into numerical, categorical, and ordinal data. For numerical data, descriptive statistics (number of subjects, mean, standard deviation, minimum, median, and maximum) will be calculated. For categorical and ordinal data, the frequency (%) will be calculated for each category. In the single-dose and multiple-dose studies, data collected at each dose of each cohort will be compared with the corresponding pooled data of the placebo group.

(1) Analysis of demographic characteristics and other baseline characteristics

Age, sex, height, body weight, BMI, race, medical history, complications, and concomitant medications will be listed by subject.

(2) Safety

AEs and adverse drug reactions (ADRs)

AEs will be coded using the Medical Dictionary for Regulatory Activities (MedDRA, version 20.0 or higher). AEs will be listed by subject, including such data as the timepoints of occurrence/disappearance, term used by the reporter, preferred term, system organ class (SOC), severity, seriousness, relationship to the investigational drug or comparator, and outcome. All AEs that occurred before the start of administration will be classified into baseline AEs and presented only in the list. In contrast, all AEs that occurred or became aggravated after the investigational drug or comparator administration will be classified into treatment-emergent adverse events (TEAEs), and these will be tabulated. In the tabulation, the number of subjects with TEAEs and the incidence and number of TEAEs will be summarized.

TEAEs will be tabulated, as shown below.

- Tabulation by SOC and preferred term
- Tabulation by SOC, preferred term, and severity
- Tabulation by SOC, preferred term, and relationship to the investigational drug

A list will be prepared for TEAEs leading to discontinuation of administration and serious TEAEs.

• Vital signs and laboratory tests

For vital signs (systolic and diastolic blood pressure, pulse rate, and body temperature) and laboratory data (hematology, biochemistry, coagulation test, and urinalysis), descriptive statistics will be calculated for values at each time point and changes from baseline. Urinalysis data will be listed by subject for each time point. Data outside of the reference range will be indicated via an attached flag in the list.

• 12-lead ECG

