Descriptive statistics will be calculated for 12-lead ECG data, for each timepoint. Data outside of the reference range will be indicated via an attached flag in the list.

(3) Pharmacokinetics

For the plasma concentrations of unchanged edaravone, sulfate conjugate, and glucuronide conjugate, descriptive statistics will be calculated by dose for each time point and time after dosing. In addition, descriptive statistics will be calculated for the PK parameters (e.g.,  $C_{max}$ ,  $t_{max}$ , AUC, and  $t_{1/2}$ ) of unchanged edaravone, sulfate conjugate, and glucuronide conjugate by dose.

- Dose proportionality will be assessed using the  $C_{max}$ ,  $AUC_{0-\text{last}}$ , and  $AUC_{0-\infty}$  (except for Cohort S3-2) of unchanged edaravone, sulfate conjugate, and glucuronide conjugate collected in Part 1, using a power model. In addition, the linearity will be evaluated using a lack-of-fit test.
- The effect of food on the PK parameters of edaravone will be assessed using the  $C_{max}$ ,  $AUC_{0-\text{last}}$ , and  $AUC_{0-\infty}$  of unchanged edaravone, sulfate conjugate, and glucuronide conjugate in Cohorts S3-1 and S3-2. The geometric mean ratio (fed/fasting conditions) and the 90% confidence interval will be calculated via analysis of variance, using the data after log transformation under fed and fasting conditions and the subjects as factors.
- The ratio of the  $C_{trough}$  (plasma concentration at the end of the dosing interval) of unchanged edaravone, sulfate conjugate, and glucuronide conjugate for each day of dosing to those after the last dose will be calculated for each subject in Part 2, and the geometric mean and 95% confidence interval will also be calculated.
- The linearity factor (LF) will be calculated to assess the linearity of unchanged edaravone, sulfate conjugate, and glucuronide conjugate after multiple doses in Part 2.

$LF = AUC_{0-T} \text{ (last dose)} / AUC_{0-\infty} \text{ (first dose)}$

T: Dosing interval

- The ratio of accumulation (RA) will be calculated to assess the accumulation of unchanged edaravone, sulfate conjugate, and glucuronide conjugate after multiple doses in Part 2.

$RA = AUC_{0-T} \text{ (last dose)} / AUC_{0-T} \text{ (first dose)}$

T: Dosing interval

(4) Pharmacodynamic assessment

For PD assessments, the Statistical Analysis Plan and report will be prepared separately.

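### Does leaving change from baseline out of the 12-lead ECG sentence in Protocol 13.4(2) weaken the QTcF safety analysis?

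*Protocol*

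**What the plan says.** Protocol section 13.4 opens by fixing the statistics for numerical data: "descriptive statistics (number of subjects, mean, standard deviation, minimum, median, and maximum) will be calculated". Under (2) Safety, the item on vital signs and laboratory tests reads "descriptive statistics will be calculated for values at each time point and changes from baseline". The 12-lead ECG item that follows reads "Descriptive statistics will be calculated for 12-lead ECG data, for each timepoint", and adds only that out-of-range values are flagged in the listing.

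Several other places bear on the point:

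- Section 5.4.1 lists the 12-lead ECG among the safety endpoints, and section 9.2.4.4 has QTcF recorded each time one is taken.
- Section 13.3 [1] fixes the baseline for safety and PD data: "Unless otherwise specified, the baseline for these assessments is the last data measured prior to the start of study drug administration".
- Section 13.1 sends detailed procedures to a separate SAP and states that "all individual subject data will be listed".
- Section 8.4(3) stops cohort transition, unless there is a reasonable ground not to, when "At least 1 subject in the active group has any of the following 12-lead ECG results in one cohort". One of the results is "Increase in QTcF by" at least 60 ms from baseline; another is an absolute QTcF of 500 ms or more.
- Section 9.2.6 restricts Holter recording: "For Cohorts S4, S5, and S6". Section 13.4(4) gives the PD analysis its own SAP and report.

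**The concern.** Two adjacent items in one section treat parallel safety data differently, and the quantity left out for the ECG is one the protocol itself relies on in 8.4(3). Read literally, the ECG tables would hold only observed values at each time point. Such values do not show how far individual subjects moved. A small shift in everyone and a large rise in one subject can give the same table.

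The Holter analysis does not fill the gap everywhere, because it covers three cohorts only. In the remaining single-dose cohorts and in all of Part 2, QTcF comes from the 12-lead ECG alone. If change were never summarised, a reader of those tables would have to turn to the individual listings to see its spread, and the comparison with pooled placebo promised in 13.4 could not be made on that scale.

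**Working it through.** **How many subjects depend on the 12-lead ECG.** The inputs are the cohort sizes in Tables 1 and 2 (section 8.3.1) and the Holter restriction in 9.2.6. S3-1 and S3-2 are the same subjects and count once.

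- Without Holter: S1, S2, S3 and S7 give 4 × 8 = 32; M1 and M2 give 2 × 9 = 18; total 50. Of these, 4 × 6 + 2 × 6 = 36 are active and 4 × 2 + 2 × 3 = 14 are placebo.
- With Holter: S4, S5 and S6 give 3 × 8 = 24.
- 50 + 24 = 74, which agrees with section 6.1.

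**What by-timepoint statistics can hide.** The QTcF values here are invented, because the protocol gives none. Take six active subjects with baselines 375, 385, 395, 405, 415 and 425 ms.

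- Scenario A: all six rise by 5 ms, giving 380, 390, 400, 410, 420, 430.
- Scenario B: the first rises by 55 ms and the other five fall by 5 ms, giving 430, 380, 390, 400, 410, 420.

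The two post-dose sets contain the same six numbers, so every statistic named in 13.4 agrees. The SD is √[(25² + 15² + 5² + 5² + 15² + 25²)/5] = √350 = 18.7 at both times.

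| Statistic | Baseline, A and B | Post-dose, A and B | Change, A | Change, B |
|---|---|---|---|---|
| n | 6 | 6 | 6 | 6 |
| Mean | 400 | 405 | 5 | 5 |
| SD | 18.7 | 18.7 | 0 | 24.5 |
| Minimum | 375 | 380 | 5 | -5 |
| Median | 400 | 405 | 5 | -5 |
| Maximum | 425 | 430 | 5 | 55 |

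In B the mean change is (55 - 5 × 5)/6 = 30/6 = 5 and the SD is √[(50² + 5 × 10²)/5] = √600 = 24.5. So the loss of information is possible in principle.

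**What the tables still show.** With complete data, the mean change is the difference of the two means: 405 - 400 = 5 ms. The largest rise is also bounded, because no subject can rise by more than the post-dose maximum minus the baseline minimum: 430 - 375 = 55 ms. Scenario B sits exactly on that bound, so it is the most extreme single rise this table allows, and it is below the 60 ms criterion. What the tables do not give is the SD, the median and the actual extremes of change.

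**Whether the sections conflict.** Section 8.4(3) asks whether at least one active subject meets a criterion. That is answered from each subject's own record during the study. It uses no table from 13.4, which describes the analysis of the collected data. The two sections do different jobs and do not contradict each other.

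**Whether the ECG wording excludes change.** It refers to ECG data at each time point and does not limit this to observed values. A change score is itself reported by time point, and its baseline is fixed in 13.3 [1]. Nor is 13.4 written as an exhaustive table specification. Sensory tests are a safety endpoint in 5.4.1 but have no item of their own in 13.4(2). Urinalysis, which 9.2.4.2 describes as sediment and qualitative tests, is included among the data to be summarised as change and is then also assigned to a listing. A difference in wording between two items of such a section is weak evidence of intent.

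**The case for a change.** The best argument for a change is that the protocol did not leave ECG summaries to the SAP. It wrote them into 13.4, and more narrowly than the item beside them, while only the PD analysis is expressly handed to a separate plan. Section 13.5 then treats this section as the reference from which changes must be justified. The in-study rule covers active subjects only and would not react to the 55 ms rise in scenario B. At 430 ms, that subject is also below the 450 ms QTc exclusion limit in 3.2, and might not be flagged in the listing, depending on a reference range the protocol does not state. Adding the words would cost almost nothing.

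Much of this stands as description: the wording is uneven, the tables as named would not show the spread of change, and aligning the two items would be harmless. It does not show that the plan goes wrong. Sections 13.1 and 13.3 both send detail on the handling and analysis of safety data to later documents, and a change column for an ECG parameter with a defined baseline is what an analyst would add by habit. Scenario B was built as an exact rearrangement of scenario A, so it shows that such a tie can occur, not that one is likely. Even then, six active subjects per cohort and a full listing leave the 55 ms rise in plain view.

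**Conclusion.** No change to the plan is called for. The difference in wording in 13.4(2) is real, but it is a gap in table detail that the SAP would be expected to fill. It is neither an error nor a contradiction with 8.4(3).

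If the SAP added nothing, the effect would be limited to descriptive tables lacking the SD, median and range of within-subject QTcF change. This would matter most for the 50 subjects without Holter data. Mean change could still be derived, the largest rise could be bounded, every individual value would be listed, and the QTcF criteria would still be applied to each active subject. The safety conclusion would remain sound. Evaluation of QTcF prolongation as an objective is tied in 5.4.3 to the Holter data from S4 to S6, the cohorts with the highest tentative single doses in Table 1, under a separate analysis plan.

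This rests on three assumptions: ECG data are essentially complete (needed to derive mean change and the bound from the tables), the listings promised in 13.1 are produced, and the SAP, which is not shown, does not restrict ECG summaries to observed values. Using the vital-signs wording for the ECG as well would be an optional tidying only.

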#### Investigational drug:

Edaravone powder will be dissolved or suspended in polyvinyl alcohol (Japanese Pharmaceutical Excipient) or a mixture of polyvinyl alcohol (Japanese Pharmaceutical Excipient) and xanthan gum (Japanese Pharmaceutical Excipient), and used as an oral solution or suspension.

- Cohorts S1, S2, S3, S5, S6, S7, M1, and M2: Polyvinyl alcohol
- Cohort S4: Polyvinyl alcohol and xanthan gum

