##### (1) Part 1 (single-dose study)

A single oral dose of the study drug will be given to subjects under fasting conditions in the morning or 30 minutes after breakfast. In Cohort S3-2, subjects in Cohort S3-1 will be given the same study drug that is allocated in Cohort S3-1 in a single oral dose after at least a 4-day washout period. Doses of Cohort S2 and thereafter are tentative. Based on the PK data obtained up to 24 hours post-dose and the safety data obtained up to 48 hours post-dose of the previous cohort, the sponsor and a medical expert will examine and determine the dose with the agreement of the investigator, such that the exposure of the minimum toxic dose (10,226 ng/mL for  $C_{max}$  and 1,226 ng•hr/mL for  $AUC_{0-24hr}$  in a free base form) is not exceeded. However, the highest dose in Part 1 shall not exceed 7,200 mg. The common ratio between the dose and the estimated mean  $C_{max}$  and  $AUC_{0-24hr}$  should be  $\leq 5$  between successive cohorts.

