**Table 1 Dose, Dosing Regimen, and Duration (Single-dose study [Part 1])**

Cohort	Dose	Condition of administration	Race	Duration	No. of subjects	
					Edaravone	Placebo
S1	60 mg	Fasting	Japanese	1 day	6	2
S2	240 mg 			1 day	6	2
S3-1	800 mg 			1 day	6	2
S3-2				1 day		
S4 	1,600 mg 			1 day	6	2
S5	2,400 mg 	Fasting	Caucasian	1 day	6	2
S6	3,600 mg 			1 day	6	2
S7 	800 mg 			1 day	6	2

1) Tentative doses are presented. The dose will be determined based on the PK and safety data collected up to the previous cohort.

2) For Cohort S4, polyvinyl alcohol and xanthan gum will be used as vehicles. Cohort S4 can be started using the same timing as Cohort S3-2.

- 3) The dose in Cohort S7 will be the same as that in Cohorts S3-1 and S3-2. Cohort S7 can be started at using same timing as Cohort S3-1.
- 4) A dose lower than in the previous cohort can be selected if it is judged that assessment of PK and safety at the maximum dosage not exceeding the exposure of the minimum toxic dose has been completed by the previous cohort.

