### 13.5 Changes in the Statistical Analysis Plan

If the statistical analysis plan in this section is changed prior to data lock, both the details of the change and reason will be specified in the Statistical Analysis Plan and Clinical Study Report. If any analytical method is changed or added after data lock, details of the change and reason will be specified in the revised Statistical Analysis Plan and Clinical Study Report, and the results will be divided into those before and after the change or addition.

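### The Part 1 dose-proportionality analysis keeps S4, the only xanthan-gum cohort, so a vehicle effect can register as lack of fit in dose

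*Protocol*

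**What the plan says.** Protocol section 13.4 (3) takes Cmax, AUC0-last and AUC0-∞ of three analytes, "collected in Part 1, using a power model. In addition, the linearity will be evaluated using a lack-of-fit test". The one exception is in the same sentence: "except for Cohort S3-2) of unchanged edaravone, sulfate conjugate, and glucuronide conjugate". It states no vehicle term, no separate handling of S4 and no fit without S4.

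Section 7.1 gives the vehicles: "Cohorts S1, S2, S3, S5, S6, S7, M1, and M2: Polyvinyl alcohol" and "Cohort S4: Polyvinyl alcohol and xanthan gum". Footnote 2 to Table 1 in section 8.3.1 repeats this: "For Cohort S4, polyvinyl alcohol and xanthan gum will be used as vehicles". In that table S4 is listed at 1,600 mg and no other cohort is. Section 8.3.1 (1) adds that "Doses of Cohort S2 and thereafter are tentative".

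**The concern.** A lack-of-fit test compares a separate mean at each dose level with the fitted line. If one level was reached only with a different vehicle, its deviation from the line is dose plus vehicle, and the data at that level cannot divide the two.

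The protocol's own logic points towards separating them. S3-2 has the same dose as S3-1 and is left out; it differs by being fed. Section 2 lists dissolution profile beside race and food as a PK question. The protocol does not name the cohort that serves that aim. S4 is the only suspension cohort with a different vehicle, so it is the natural candidate.

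PK is part of the primary objective, and the linearity assessment is one of its few inferential statements. If the test is significant with the misfit at 1,600 mg, the planned analysis cannot say whether dose or vehicle caused it.

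**Working it through.** **The plan's own numbers.** Section 6.1 gives 8 subjects per Part 1 cohort, 6 of them on edaravone: 7 × 8 = 56, and 7 × 6 = 42 on edaravone, which reproduces its Part 1 total. It says the size rests on no power calculation. No CV, vehicle ratio or test level is given.

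**Inputs.**
- From the protocol: tentative doses 60, 240, 800, 1,600, 2,400 and 3,600 mg; 6 active subjects per cohort; 12 at 800 mg because S3-1 and S7 share that dose.
- Assumed: true relation exactly log-linear; S4 alone multiplied by a vehicle ratio R; 5% level; CV 30/40/50%; pure error taken within dose levels.

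**Set-up.** With x = ln(dose), the weighted mean of x is 6.613, Sxx = Σn(x − x̄)² = 72.44, and S4 lies at x = ln 1600 = 7.378, which is 0.764 above the mean. Log-scale variance is σ² = ln(1 + CV²) = 0.0862/0.1484/0.2231.

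**Slope shift** = 6 × 0.764 × ln R / 72.44.
- R = 0.80: 6 × 0.764 × (−0.2231) / 72.44 = −0.014
- R = 0.70: −0.023

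The slope's 90% CI half-width at CV 30% is 1.684 × √(0.0862/72.44) = 0.058, so both shifts lie well inside it.

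**Share of the misfit at S4.** For any R, the fraction is 1 − 6/42 − 6 × 0.764²/72.44 = 1 − 0.143 − 0.048 = 0.81. For R = 0.80 the mean residuals in dose order are −0.004, 0.016, 0.033, −0.180, 0.048 and 0.054.

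**Noncentrality** = 6 × (ln R)² × 0.809 / σ². For R = 0.80 and CV 30%: 6 × 0.0498 × 0.809 / 0.0862 = 2.80.

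**Chance of a significant lack of fit**, noncentral F on 4 (6 levels − 2) and 36 (42 − 6) df:

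| Vehicle ratio | CV 30% | CV 40% | CV 50% |
|---|---|---|---|
| 1 (none) | 5% | 5% | 5% |
| 0.90 | 8% | 7% | 6% |
| 0.80 (or 1.25) | 20% | 13% | 10% |
| 0.70 | 49% | 29% | 20% |

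A simulation of 20,000 trials agrees: 0.202/0.135/0.101 at 0.80 and 0.490/0.286/0.205 at 0.70. Leaving S7 out (4, 30 df) gives 20%/13%/10% and 47%/28%/19%.

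**With S4 set aside** (36 subjects, 5 levels, 3 and 31 df), a vehicle effect confined to S4 cannot enter, and the rate is 5% if no other cohort differs for a reason other than dose.

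**The case against.** The strongest reply is about weight. Nothing in the protocol shows that xanthan gum changes exposure, the protocol does not spell out the form of the lack-of-fit test, and at a ratio of 0.90 the inflation is close to nothing. The 49% needs a 30% shift and the lowest CV. The slope is sound, cohort transition (section 8.4) does not use the test, and a residual plot would point to S4. All of this stands, and it keeps the point modest.

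A second reply is that a vehicle term or sensitivity fit is ordinary SAP content. That is true of such details, but section 13.4 itself fixes the data set and its single exception. An SAP that follows it inherits the problem.

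Third, the proposed set is not fully clean. S7 is the Caucasian cohort, and S1 appears to be a solution, since section 7.1 gives it the solution comparator. With S4 out, a ratio of 0.80 at S1 would move the slope by +0.047, against a half-width of 0.060 at CV 30%, and give 12%/9%/7% rejection. This is right. It makes the return to 5% conditional, but it does not remove the aliasing at S4.

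Fourth, doses are tentative, and footnote 4 to Table 1 lets S5 or S6 go below the previous cohort's dose, so S4 need not stay alone at its level. The figures therefore hold for the planned doses only.

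**Conclusion.** The point holds. As written, S4 is in the power model and the lack-of-fit test, and on the planned doses its vehicle is fully aliased with the 1,600 mg level. A moderate vehicle effect (ratio 0.70 to 0.80) would raise the chance of a false lack-of-fit signal from 5% to between 10% and 49%, depending on the CV; a ratio of 0.90 would scarcely matter. These rates rest on assumed vehicle ratios, CVs and test level. The slope estimate is essentially unaffected and no decision is tied to the test. The consequence is limited to the linearity statement for three parameters of three analytes: minor to moderate, but worth correcting because the correction is nearly free.

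**What to change.** Run the power model and lack-of-fit test on the Part 1 fasting cohorts given in polyvinyl alcohol alone, or keep S4 with an indicator term so that it informs neither the slope nor the linearity test. Show the fit with S4 as an ordinary dose level as a sensitivity analysis. If the indicator is used, its coefficient may be reported as an exploratory between-cohort vehicle ratio that depends on log-linearity. State alongside how S1 and S7 are treated. No cohort or dose changes.

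Section 13.5 already provides the route before data lock: "both the details of the change and reason will be specified in the Statistical Analysis Plan and Clinical Study Report".

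Costs:
- Numerator df fall from 4 to 3, and a departure confined to 1,600 mg would show only in the sensitivity fit.
- The slope's 90% CI half-width at CV 30% goes from 0.058 to 0.060 (3.4% wider before rounding).
- Power for smooth curvature is not lost. If the local slope drifts by 0.4 from 60 to 3,600 mg, it is 22%/14%/11% with S4 (assuming no vehicle effect) and 25%/16%/12% without, at CV 30/40/50%.
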